The results from this pilot study will provide the foundation for further study to discern the most effective types of exercises to improve bone strength and ultimately reduce the risk of fracture. The current exercise recommendations for the prevention and treatment of osteoporosis have evolved from preclinical research (i.e., animal models) on the loading characteristics of an activity that are important for the activation of bone formation (i.e., dynamic, high magnitude bone-loading forces, high strain rate). The current application is focused on how the mode of exercise can influence an acute bone biomarker response, which could impact bone strength and fracture risk long-term. In the short-term, this study will be informative to

determine if mode of exercise is an important determining factor in the bone biomarker response to exercise, which will aid in the design of future trials. Longer-term, if a difference in mode of exercise is found, this research will be used to determine what discrepancy exists between modes of exercise, and how different exercise programs can be designed to maximize benefit to bone. This is especially relevant to older Veterans, as service-related orthopedic limitations do not always allow for all forms of exercise to be completed safely, but this research could lead to strategies to enhance the benefits of exercise on osteoporosis prevention for both Veterans and the general public.

H. References:

- 1 Nagle, K. B. & Brooks, M. A. A Systematic Review of Bone Health in Cyclists. *Sports Health* **3**, 235-243, doi:10.1177/1941738111398857 (2011).
- 2 Kohrt, W. M., Bloomfield, S. A., Little, K. D., Nelson, M. E. & Yingling, V. R. American College of Sports Medicine Position Stand: physical activity and bone health. *Med. Sci. Sports Exerc.* **36**, 1985-1996 (2004).
- 3 Barry, D. W. & Kohrt, W. M. BMD decreases over the course of a year in competitive male cyclists. *J. Bone Miner. Res.* **23**, 484-491 (2008).
- 4 Sherk, V. D. *et al.* Bone loss over 1 year of training and competition in female cyclists. *Clin J Sport Med* **24**, 331-336, doi:10.1097/JSM.0000000000000050 (2014).
- 5 Klesges, R. C. *et al.* Changes in bone mineral content in male athletes. Mechanisms of action and intervention effects. *Journal of the American Medical Association* **276**, 226-230 (1996).

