Exclusion criteria include: **1)** impaired renal function, defined as an eGRF of <60 mL/min/1.73m²³³ **2)** hepatobiliary disease, defined as liver function tests (AST, ALT) >1.5 times the upper limit of normal; **3)** thyroid dysfunction, defined as an ultrasensitive thyroid stimulating hormone (**TSH**) <0.5 or >5.0 mU/L; **4)** serum Ca <8.5 or >10.3 mg/dL; **5)** serum 25(OH)D <20 ng/mL; **6)** uncontrolled hypertension, defined as resting systolic blood pressure (**BP**) >150 mmHg or diastolic BP >90 mmHg; **7)** history of type 1 or type 2 diabetes; **8)** cardiovascular disease; defined as subjective or objective indicators of ischemic heart disease (e.g., angina, ST segment depression) or serious arrhythmias at rest or during the graded exercise test (**GXT**); volunteers who have a positive GXT can be re-considered after follow-up evaluation, which must include diagnostic testing (e.g., stress echocardiogram or thallium stress test) with interpretation by a cardiologist; **9)** anemia, defined as a serum hemoglobin <12.1 g/dL for women and <14.3 g/dL for men; **10)** fracture in the past 6 months; **11)** current diagnosis or symptoms of COVID-19. In the event of abnormal BP, liver function, TSH, 25(OH)D, or hemoglobin values, volunteers can be reassessed, including after appropriate follow-up evaluation and treatment by a primary care provider. Those who have experienced symptoms of COVID-19 or have been formally diagnosed will be allowed to participate once symptoms have resolved and they are approved to return to exercise by their primary care provider. This study will not enroll vulnerable populations. Non-English speakers will also be excluded due to the need to constantly communicate verbally to ensure participant safety during exercise testing.

C. Study Design and Research Methods

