Blinding and randomization. Neither the research team nor the participants can be blinded to the mode of exercise. However, samples will be labeled in a manner that ensures the individual analyzing the samples will be blinded to the test condition. The order of the testing condition will be randomized and counterbalanced. Once a participant has been verified to meet enrollment criteria and initial sign-off by the study physician and the primary investigator has occurred, participant details (sex, ID number) will be entered into REDCap, which houses the randomization scheme (developed by the GRECC biostatistician). The randomization scheme will include allocation by sex, but not by race/ethnicity or age due to the small sample size.

Submaximal exercise sessions. Each participant will complete 2 exercise sessions that vary by mode: cycling at 70-80% HRmax and treadmill at 70-80% HRmax. HRmax will come from the GXT at screening. Each session will be 60 minutes in duration (plus a 5-minute warm-up at ~50% of HR max) and sessions will be at least 1 week apart. Sources of variance in the CTX response to exercise (primary outcome) other than mode of exercise may include pre-exercise Ca ingestion and the time of day the test is performed, because CTX has a diurnal rhythm.³⁵ To minimize variance from these sources, all exercise tests will be performed in the morning after a calcium-controlled meal and participants will be asked to avoid taking Ca supplements and multi-vitamins for 24 h before a test. Participants will be fasted when they return for the 24-hour blood draw.

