Figure 4. Timing of blood and urine collections before and during 60 minutes of exercise and 4 hours of recovery.

D. Description, Risks and Justification of Procedures and Data Collection Tools:

Potential Risks:

Exercise: The risks of this study are those of any exercise testing or exercise program and include musculoskeletal injury, falls during exercise, and symptoms of unknown underlying cardiac disease.

Ionizing radiation: Participants will be exposed to radiation from the dual-energy x-ray absorptiometry (DXA) testing that will occur at screening. Like any x-ray imaging modality, the DXA system used in this study exposes the participant to ionizing radiation. The ionizing radiation from the DXA scan of the total body, pelvic region, and lumbar spine is roughly the equivalent dose of 4 days of radiation exposure from the environment.

Venipuncture and IV: There is a small risk of local hematoma, infection, syncope, and thrombosis associated with intravenous blood sampling.

Confidentiality and privacy: The use of questionnaires, interviews, and collection of personal medical information poses a risk to confidentiality and privacy and may cause embarrassment.

Psychological risks are minor and include frustration with exercise program and frequent visits to the research facility.

Sources of Materials: Data from each participant's medical history will be acquired from patient interview and from the patient medical record to assure they are appropriate for an exercise study. Data will be acquired with the patient's permission during the screening process. Once the patient is enrolled in the study, additional information may be acquired from the participant's medical record and recorded in the study database. This includes information such as medical history and medications. Participants will also be interviewed for additional information such as exercise history, history of bone and muscle problems, as well as sedentary behavior. Blood samples will be collected at the time of enrollment for assessment of renal function and electrolytes and additional samples will be stored for future analysis of bone turnover markers and inflammatory mediators.

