All adverse events (AE's) occurring during the study will be collected, documented, and reported to the PI. Every month the investigators will review AE forms for the month. The study investigators will follow all AE's to the point of a satisfactory resolution. All AEs will be reported to the VA and COMIRB in accordance with institutional policies. Serious adverse events (SAEs), whether or not related to the study protocol, will be reported (within 24 hours) to the local IRB. Any recommended changes to the protocol as a result of monthly monitor meetings will be submitted and approved by the IRB prior to implementation. A summary of the SAEs that occurred during the previous year will be included in the annual progress report. The

principal investigator will be responsible for safety monitoring and review de-identified data on a quarterly basis and as necessary.

E. Potential Scientific Problems:

Recruitment may be a challenge due to the limited number of older women Veterans and the physical activity requirements of potential participants. However, the PI is involved with a clinical exercise program that includes women Veterans in the appropriate age range, and they will be provided the option to volunteer for the proposed research. Additionally, our research group has performed targeted recruiting through our local Community-Based Outpatient Clinics (CBOCs), the Corporate Data Warehouse (CDW), and VA Information and Computing Infrastructure (VINCI) and we have been successful in recruiting similar participants for other VA research studies.

F. Data Analysis Plan:

Sample size and statistical analysis plan. The primary outcome is the change in CTX from pre-exercise to the end of exercise. The change in CTX is hypothesized to be positive for both conditions. With 30 subjects, we will have at least 80% power to detect a change of 0.12 ng/mL or greater between conditions. The study is not powered to detect subgroup differences on the effects of sex. However, exploratory analyses will be conducted to be able to power future studies and to generate hypotheses. To achieve 15 completers per sex, 18 men and 18 women will be enrolled based on an expected drop-out rate of ~20%.

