The effects of treadmill versus cycling exercise on the change in CTX will be evaluated using linear contrasts in a repeated measures maximum likelihood model with all available data. We have utilized this approach in similar experiments,^{9,37,38} and it is conceptually identical to repeated measures analysis of variance but avoids the deletion of cases with missing assessments. Estimates are unbiased under the assumption that missing data are missing at random. Linear contrasts will be used to estimate within-condition changes and between-condition differences in changes over the 60-minute exercise bouts and the recovery periods separately. Primary comparisons will include up to the 24-hour blood draw. Secondary analyses will be conducted utilizing the 48-hour timepoint, but results will be interpreted with caution due to the potential for low sample size. This analysis will be repeated for secondary outcomes (change in iCa, tCa, PTH). The distributions of the outcome measures will be checked. If there are severe departures from a normal distribution, transformations (e.g., natural logarithm) will be applied as appropriate to achieve an endpoint that is approximately normally distributed. To minimize missing data, all participants will be informed of the importance of complete follow-up and encouraged to complete the study per the protocol. Although statistical methods can be used to adjust for missing data, these methods rely on the untestable assumption that data are either **1)** missing completely at random, for which no adjustment is needed, or **2)** missing at random, for which the effect of the “missingness” can be removed through statistical modeling. We will instead focus on preventing missed exercise tests and samples. Due to the mechanistic nature of the studies and the use of the results to guide decisions about a future randomized controlled trial, no adjustments for multiple comparisons will be performed. All analyses will be conducted using SAS software version 9.4 M4 (SAS Institute Inc, Cary, NC, USA) and a p-value ≤ 0.05 defining statistical significance. For the exploratory analyses in SA2, we will use the same statistical approach as SA1 while including sex in the maximum likelihood model. Results will be interpreted with caution due to the low sample size, and will be used to generate hypotheses for future research.

G. Summarize Knowledge to be Gained:

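### Drugs that alter bone turnover are neither an exclusion nor handled in the analysis of a CTX-primary study, so a null result could be ambiguous

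*Combined protocol and SAP*

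**What the plan says.** **Eligibility.** IV.B gives 11 numbered exclusions. Several concern bone or calcium metabolism: renal function, TSH, serum calcium, 25(OH)D and "fracture in the past 6 months". None concerns a drug. IV.D (Research Risk) separately excludes a T-score of -2.5 or lower at the lumbar spine or femoral neck, as protection against bony injury during the exercise tests.

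**Control of CTX variance.** IV.C (Submaximal exercise sessions) names calcium intake and time of day as possible sources of variance other than mode. It controls them with morning testing, a calcium-controlled meal and 24 hours without calcium supplements or multivitamins. Drugs are not mentioned.

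**Medication data.** IV.D (Sources of Materials) allows further details to be taken from the medical record after enrolment: "This includes information such as medical history and medications". No eligibility or analysis use is given for them.

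**Endpoint, design and power.** IV.F states: "The primary outcome is the change in CTX from pre-exercise to the end of exercise". IV.C states: "Each participant will complete 2 exercise sessions that vary by mode: cycling at 70-80% HRmax and treadmill at 70-80% HRmax". On size, IV.F states: "With 30 subjects, we will have at least 80% power to detect a change of 0.12 ng/mL or greater between conditions". The model in IV.F contrasts the two modes with repeated measures by maximum likelihood. Sex enters only for the exploratory second aim, and medication does not enter at all.

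**The concern.** The protocol treats CTX as a reflection of bone resorption and works to remove other influences on it. Drugs prescribed to suppress or stimulate bone turnover act on that same process, and the plan as written would admit people taking them. Users are plausible: participants are 60 or over, half are women, and section III refers to older Veterans who exercise to reduce osteoporosis risk.

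The crossover cancels stable differences in level between people. It cannot restore a mode difference that a drug has reduced in both sessions. With 30 participants, a few such people could leave a null CTX contrast with two explanations: mode does not matter, or some participants could not show that it does. IV.F says the results will guide a later randomized trial, so the distinction matters. Without a pre-specified rule, any later removal of users would be post hoc. Nor does any rule require medication to stay the same between sessions, and a drug started or stopped between them would not cancel.

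**Working it through.** **1. The plan's own figure.** IV.F gives n = 30, a difference of 0.12 ng/mL, power of at least 80% and "a p-value ≤ 0.05 defining statistical significance". It gives no SD and no sidedness, so the 80% cannot be reproduced, only inverted. I assume a two-sided paired t-test with power from the noncentral t, df = 29, critical value 2.045. Power of exactly 80% needs a noncentrality of 0.12 × √30 / SD = 2.899, so the SD of the paired difference is 0.2267 ng/mL (standardized effect 0.12 / 0.2267 = 0.53). Because the plan says at least 80%, this SD is an upper bound under these assumptions.

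**2. Dilution, assuming 0.12 is the effect in non-users.** Let f be the share of users, let users have no mode difference, and let their SD be u times that of non-users.

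- Mean contrast = 0.12 × (1 − f)
- Variance = (1 − f) × 0.2267² + f × (u × 0.2267)² + f × (1 − f) × 0.12²

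For 3 users (f = 0.10) and u = 1, the mean is 0.12 × 0.90 = 0.108. The variance is 0.05141 + 0.10 × 0.90 × 0.0144 = 0.05271, so the SD is 0.2296. Noncentrality is 0.108 × √30 / 0.2296 = 2.58, and power is 70.2%.

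| Users of 30 | Mean contrast | Power, u = 1 | Power, u = 0.3 |
|---|---|---|---|
| 0 | 0.120 | 80.0% | 80.0% |
| 1 | 0.116 | 76.9% | 78.2% |
| 3 | 0.108 | 70.2% | 74.2% |
| 6 | 0.096 | 59.2% | 67.5% |

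**3. Partial blunting.** If users keep half the mode difference, the mean is 0.12 × (1 − f/2) and the last variance term becomes f × (1 − f) × 0.06². With 3 users the mean is 0.114. Power is 75.6% if their SD is unchanged and 78.8% if it halves too.

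**4. The other reading of 0.12.** If 0.12 is the mean difference among everyone enrolled, the mean contrast stays at 0.12 and the non-user effect is 0.12 / (1 − f). The last variance term is then f × (1 − f) × [0.12 / (1 − f)]². Power (u = 1 / u = 0.3) is 78.8% / 82.4% with 3 users and 77.3% / 84.4% with 6. It stays near 80%.

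**5. Sensitivity to the SD.** With an assumed SD of 0.20 in step 2, 3 fully blunted users leave 80.3% (u = 1) or 83.8% (u = 0.3).

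**6. Dropping users from the analysis.** At 0.12 and SD 0.2267, power is 75.4% with 27 people left and 70.0% with 24.

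**The case against.** The strongest objection is to the consequence. A reader might infer that users would dilute the contrast and that the claim "we will have at least 80% power to detect a change of 0.12 ng/mL or greater between conditions" is therefore wrong. The documents do not support that. They contain no data on how such drugs affect the CTX response to exercise, no SD and no expected number of users. Drugs that stimulate turnover need not act in the same direction as those that suppress it. The power sentence can also be read as a detectable mean among those enrolled, in which case step 4 shows little change. All of this stands, and it limits the power figures to an illustration.

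A reader might also infer bias between cycling and treadmill. That does not follow either: each person is their own control, and stable use is present in both sessions.

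There are partial safeguards. Participants must be healthy, they give a medical history, the study physician signs off, and the T-score rule removes people with low current bone density. If that leaves few users, the effect is small. These points narrow the gap, but none is a medication rule, and a treated person above the T-score threshold passes all of them.

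Finally, this is a pilot that expects difficulty recruiting older women Veterans, so broad eligibility is defensible. That is a reason to prefer the analysis route over exclusion if recruitment is tight. It is not a reason to leave the matter unstated.

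**Conclusion.** The omission is confirmed: neither the eligibility rules, the pre-test controls nor the analysis model addresses drugs that alter bone turnover. The consequence is possible attenuation and heterogeneity of the primary contrast, which would make a null result ambiguous.

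Its size is unknown. Under the least favourable reading (0.12 ng/mL applies to non-users, users show no mode difference, SD 0.2267), power could be about 77-78% with 1 user and 70-74% with 3. Partial blunting, a smaller SD or the other reading of 0.12 reduces the loss or removes it. The stated 80% is neither verified nor refuted. The point is worth acting on because the remedy is cheap and fits the protocol's existing effort to control influences on CTX.

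**What to change.** Preferred: add a criterion on bone-active medication to the IV.B list, with the drugs and the time window set by the study physician. It costs one protocol line and a somewhat smaller recruitment pool. The loss should be limited, because IV.D already excludes people who meet the T-score definition of osteoporosis.

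At minimum, without changing eligibility:

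- Record these medications for every participant at screening, and any change between the two sessions. IV.D now says only that such information may be acquired, so this is a small added task.
- Report the number of users.
- Pre-specify in IV.F a sensitivity analysis of the CTX mode contrast that leaves users out.

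The sensitivity analysis costs one extra model and nothing in recruitment. It helps interpretation more than power: dropping 3 of 30 leaves about 75%, against 70-74% if they stay in and are fully blunted. Only the entry criterion, with 30 non-users completing, keeps power at the stated level under the assumptions in the working.

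IV.F should also give the SD behind the 80% and say which population the 0.12 ng/mL refers to.

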Participants will arrive between 0900h and 1000h. After vital signs are obtained, an intravenous catheter for blood sampling will be positioned in a forearm vein. Participants will remain rested in a semi-recumbent position for ~15 minutes; a blood sample will be obtained at the end of this interval. After voiding, body weight (in hospital gown) will be measured and, after dressing, participants will move to the cycle ergometer or treadmill and remain seated or standing for 5 minutes before exercise. A second pre-exercise blood sample will be obtained immediately before exercise. This sampling paradigm will enable us to address the contention that positional changes have not been adequately considered in evaluating the changes in plasma volume in response to cycling and running.³⁶ Participants will be allowed deionized water *ad libitum* during exercise and recovery. Water consumption and urine volumes will be recorded for calculation of plasma volume changes. They will return between 1000h and 1100h the next morning after a 10- to 12-h fast for the 24-h blood sample.

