Blood collections (Fig 4) and assays. For each of the exercise tests, two pre-exercise blood samples will be obtained as described in the preceding paragraph. Blood samples (10 mL each) will be obtained after 15, 30, 45, and 60 minutes (exercise), and at 75, 90, 120, and 300 minutes during recovery, and 24 hours after the end of exercise. An additional blood sample 48 hours after exercise will be available as an optional procedure for analysis of iCa, P1NP, and CTX. After exercise, participants will remain in a semi-recumbent position for the duration of recovery. Blood samples will be processed by the CTRC Core Laboratory (partial off-site waiver will be pursued) and stored at -80°C. Samples from all exercise sessions for an individual will be analyzed in batch to minimize batch effects. The exceptions to this will be the parameters measured in real time (hematocrit (**HCT**), iCa, pH) during the study visits by the iSTAT analyzer (Abbot Point of Care, Princeton, NJ). Serum (or plasma) assays will include: **1)** PTH by immulite two-site enzyme immunoassay (Siemens, Erlangen, Germany; CTRC Core Lab), **2)** CTX by chemiluminescence (Immunodiagnostic Systems, Boldon Business Park, UK; CTRC Core Lab), **3)** P1NP by chemiluminescence (Immunodiagnostic Systems; CTRC Core Lab), and **4)** tCa by indirect ion-selective electrode (Beckman Coulter Inc; UCH Clinical Lab). Laboratories where assays will be conducted are CAP and CLIA certified. Laboratory-specific intra- and inter-assay coefficients of variations are generally lower than those determined by the manufacturers. PTH, CTX, iCa, and tCa, concentrations during and after exercise will be adjusted for shifts in plasma volume as previously described.⁸ These outcomes cannot be assayed in a VA laboratory due to the lack of the necessary combined analysis system. Performing each assay individually in a wet lab would double the blood required, increasing participant burden and risk.

Feasibility measures. Participants will be asked to rate multiple aspects of their experience, including preference for each mode of exercise, ease of getting to and from the exercise facility, and their likelihood of participating in a center-based exercise program that would require multiple trips to the VA facility several times per week over multiple months. This information will be used to inform future intervention designs.

[figure not shown]

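### If the within-mode contrasts run to 24 h, that change compares a fed baseline with a fasted sample, has no rest session, and cannot be attributed to exercise; the between-mode contrast is not biased

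*Combined protocol and SAP*

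**What the plan says.** Section IV.C (Submaximal exercise sessions) sets the conditions for the exercise day: "all exercise tests will be performed in the morning after a calcium-controlled meal". On timing it says "Participants will arrive between 0900h and 1000h", and it lists no meal between arrival and the two pre-exercise samples. For the following day it says "Participants will be fasted when they return for the 24-hour blood draw" and, in the next paragraph, "They will return between 1000h and 1100h the next morning after a 10- to 12-h fast for the 24-h blood sample". Each participant has two sessions, one cycling and one treadmill, in randomised and counterbalanced order. Neither is a resting session.

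Section IV.F plans linear contrasts to estimate "within-condition changes and between-condition differences in changes over the 60-minute exercise bouts and the recovery periods separately". It then says "Primary comparisons will include up to the 24-hour blood draw" and applies one general rule, a "p-value ≤ 0.05 defining statistical significance". It does not mention feeding state.

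The primary outcome (IV.F) is the CTX change from pre-exercise to end of exercise. The only hypothesis at 24 h is H1b in Section I, which compares P1NP between the two modes.

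**The concern.** A change from baseline is attributable to exercise only if nothing else that moves the marker changes systematically between the two samples, or if a control session removes it. At 24 h the feeding state changes by design and there is no control session. The protocol itself treats pre-exercise calcium intake as a source of variance in the CTX response and standardises the meal for that reason, yet the 24-h sample is taken under a different condition from its baseline.

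What is at stake is interpretation. A significant 24-h rise or fall within one mode could be reported as a lasting effect of that exercise when some or all of it is the change from fed to fasted. IV.F says the results will guide decisions about a future randomised trial, so such a reading could be carried forward.

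**Working it through.** **The plan's own figure.** The only quantitative claim is at least 80% power with 30 participants for a 0.12 ng/mL between-condition difference in CTX change. No SD is given, so it can only be inverted. The normal approximation gives an SD of the paired difference of 0.12 × √30 / (1.960 + 0.842) = 0.235 ng/mL; the paired-t version gives 0.227. This concerns the end-of-exercise between-mode contrast. It says nothing about feeding and is not used below.

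**Sampling conditions side by side (IV.C).**

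| | Pre-exercise samples | 24-h sample |
|---|---|---|
| Feeding | After a calcium-controlled meal | After a 10- to 12-h fast |
| Arrival or return | 0900h to 1000h | 1000h to 1100h |
| Same in both modes? | Yes | Yes |

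Clock time is roughly matched. Feeding state is not. The interval between meal and first sample is not stated.

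**What each contrast estimates.** Write the mean 24-h change in mode m as

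D(m) = E(m) + F,

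where E(m) is the effect of exercise in that mode and F is the fasted-minus-fed shift plus any other non-exercise change.

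- Within mode: D(cycling) = E(cycling) + F and D(treadmill) = E(treadmill) + F. That is two observed means and three unknowns, so neither E can be recovered.
- Between modes: D(cycling) − D(treadmill) = E(cycling) − E(treadmill). F drops out. The same meal and fast rules apply to both sessions and the order is randomised.

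A simulated 30-person crossover with no exercise effect and no mode effect (all inputs assumed) agreed. The mean within-mode change equalled whatever offset was put in. The between-mode mean was 0.000, with rejection at about 5%.

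**Precision.** If F also varies from session to session within a person with SD s, the variance of the paired between-mode difference rises by 2s². Illustration with an assumed per-sample SD of 0.08 ng/mL (four samples per difference): √(4 × 0.08²) = 0.160. With s = 0.05 it is √(0.0256 + 0.0050) = 0.175. With s = 0.10 it is √(0.0256 + 0.0200) = 0.214. These show the mechanism only and are not forecasts for this trial.

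**Do the within-condition contrasts reach 24 h?** The contrast sentence covers exercise and recovery separately, and the 24-h sentence follows directly, which suggests yes. Against this, the blood-collection paragraph lists the 75- to 300-minute samples as recovery and the 24-h sample separately, keeps participants semi-recumbent throughout recovery, and the Figure 4 caption gives recovery as 4 hours. The text leaves the question open.

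**Timing of the draw (side point).** The timed steps total 15 + 5 + 5 + 60 = 85 minutes. Arrival at 0900h to 1000h puts the end of exercise at 1025h to 1125h at the earliest. A sample "24 hours after the end of exercise" is then due at 1025h to 1125h or later, against a return window of 1000h to 1100h.

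**The case against.** The strongest reply is that no stated claim depends on a 24-h within-mode change. H1b is between-mode, H1a and the primary outcome do not need it, and Section IV.G frames the knowledge to be gained as being about mode. IV.F says these contrasts will be estimated and names no within-mode hypothesis at 24 h. On the narrower meaning of recovery they may stop on the same day. All of this stands, and it limits the point to interpretation. It does not remove it: IV.F takes its primary comparisons to the 24-h draw under one general significance rule, and marks no 24-h estimate as descriptive.

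A reader might also infer more than the documents support.

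- That H1b or the 24-h mode comparison is biased. It is not; a common shift cancels.
- That the feeding shift can be sized, for instance as a share of the 0.12 ng/mL target. That would mean moving an end-of-exercise SD to 24 h and assuming a between-mode correlation, and the answer would follow the assumption.
- That the 24-h timing is contradictory. IV.C gives a return time, not a draw time. Someone who returns at 1100h can wait until 1125h.

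In the other direction, calling the between-mode contrast wholly unaffected would be too strong, because precision may suffer. The cancellation also covers the mode contrast only. SA2 compares the sexes within a bout, where a shift that differed by sex would not cancel; the documents give no evidence that it does.

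**Conclusion.** The point holds as a minor one about interpretation. A 24-h within-mode change, if tested under the general rule, would combine exercise with the change from fed to fasted, and this two-session design cannot separate them. That conclusion rests on the plain reading that the pre-exercise samples are fed and on the likely, but not certain, reading that the within-condition contrasts run to 24 h. The size and direction of the feeding shift are unknown from the documents, and no numeric magnitude is claimed.

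The cycling-minus-treadmill contrasts, H1a, H1b and the end-of-exercise primary outcome are not biased, provided the shift has the same mean in both sessions. Some loss of precision at 24 h is possible. The return window is a point to reconcile, not a proven contradiction.

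**What to change.** In IV.F, add a sentence or two saying that:

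- inference about exercise at 24 h rests on the between-mode difference only; and
- any 24-h within-mode change is reported as an estimate with confidence interval, without a significance claim, and labelled as confounded with feeding state.

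This needs no new visits, samples or participants. It keeps every between-mode test and the 60-minute within-mode contrasts. The cost is giving up a tested 24-h claim for each mode alone, which the design cannot support.

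Optional: clarify in IV.C how the 1000h to 1100h return window fits a sample due 24 hours after exercise ends, and record the actual draw time.
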